Official Title: Delivering Patient-Centered Adolescent Preventative Care with Training and Technology

NCT: 02764190

Unique Protocol ID: IHS-1402-10592

Date: April 28, 2016

1. Background and Rationale

Adolescents have some of the highest rates of risk behaviors of all age groups and health behaviors developed in adolescence can persist into adulthood. Health risk behaviors, such as alcohol and other drug use, smoking, unsafe sexual activity, and poor nutrition and physical inactivity are among the most common causes of adolescent illness and premature death. These behaviors carry significant risks for subsequent disease, disability, and healthcare burden. Despite these risks, health risk screening in primary care is infrequently performed and results are rarely followed by targeted intervention.

Studies have shown that electronic health risk screening is feasible and efficient in clinical practice, increases adolescents' comfort with disclosure of behavior and encourages utilization of preventive health services. Based on this evidence, electronic multi-risk behavior screening tools are being developed for adolescent care settings. However, to reduce risk behaviors, screening needs to be linked to interventions. In response to the need for screening-linked interventions, our study team has developed a web-based, electronic screening and Personalized Motivational Feedback tool which we refer to as the "Check Yourself" app. Based on motivational interviewing, a technique to mobilize personal change, Check Yourself is designed to promote healthy choices for the multiple behaviors relevant to adolescents. Building on electronic health interventions, primary care providers (PCPs) can play an essential role in helping adolescents to make healthy behavior choices.

Adolescents list PCPs among the first people with whom they would consider discussing risk behaviors, and report greater satisfaction with care when PCPs discuss these sensitive topics with them. Thus, primary care visits present a key opportunity for improving the health of adolescents. However, to take advantage of this opportunity, health systems strategies are needed that can practically be implemented in the time-pressured environment of primary care. Emerging evidence suggests that the consistency of preventive counseling can be increased through provider training and the provision of screening tools; yet, we know very little about the quality of such counseling, and if it impacts outcomes that are important to adolescent patients themselves.

In order to address these gaps, this proposal aims to test an interactive adolescent-centered PCP training (I-ACT) to increase PCPs' ability to engage and empower adolescents to make healthy behavioral choices and to stimulate patient-provider discussions around health behavior choices. We will examine the impact of our training in the presence of Check Yourself, which systematizes screening, delivers motivational feedback directly to adolescents, and generates a targeted report to PCPs summarizing youth risk behaviors and recommendations for next steps in care.

1.1. Purpose

The purpose of this study is to evaluate the perceived impact and effectiveness of our system of interventions (I-ACT with Check Yourself) among a sample of adolescents aged 13-18 drawn

from the targeted primary care clinics using a group who receives usual care as a comparison. This study has two aims:

Aim 1. To evaluate I-ACT with Check Yourself on intermediary targets: improving adolescent motivation for health, increased provision of appropriate preventive counseling, and follow-up care. We will examine the impact of I-ACT with Check Yourself on adolescent self-report of motivation for health at baseline and 3, 6 and 12 months following the primary care visit. We will also examine the impact of I-ACT with Check Yourself on the adolescent self-report of receipt of PCP-delivered risk reduction counseling at one day following the primary care visit and follow-up care at 3, 6 and 12 months following the primary care visit.

Aim 2. To evaluate the effects of I-ACT with Check Yourself on adolescent satisfaction with the provider visit, perception of patient-centeredness of care, and health risk behaviors. We will explore the impact of I-ACT with Check Yourself on health care satisfaction among adolescents and caregivers at one day following the primary care visit. We will also explore the impact of I-ACT with Check Yourself on adolescent self-report of their perception of patient-centeredness of care at one day following the primary care visit. We will examine the effect of I-ACT with Check Yourself on producing significantly lower rates of alcohol use, marijuana use, unprotected sexual activity, and depression compared to a usual care group at baseline and 3, 6, and 12 months after the primary care visit. We will also examine the effect of I-ACT with Check Yourself on producing significantly higher levels of physical activity, fruit and vegetable consumption, and seatbelt and helmet use when compared to a control group at baseline and 3, 6 and 12 months after the primary care visit.

2. Criteria for Subject Selection

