3.1. Study Design

This study will evaluate the effect of I-ACT with Check Yourself on adolescent-perceived quality of care (i.e., satisfaction and perception of PCP communication), motivation for health, and health risk behaviors using a stepped wedge study design. The study will take place in 6 participating PSPRN affiliated clinics, where the system of interventions (I-ACT with Check Yourself) will be rolled-out sequentially to the clinics, chosen in random order, over spaced time intervals (see Figure 1). We refer to pre-implementation of I-ACT with Check Yourself, as the control period and post-implementation as the intervention (i.e., case) period.

Figure 1: Stepped Wedge Study Design and Timeline

We anticipate that approximately 30% of youth approached will participate in the study. Thus, we will invite approximately 1000 adolescent/caregiver dyads to participate in the study, in order to yield 300 adolescent/caregiver dyad participants in our total sample. Upon enrollment, caregiver participants will be asked to complete a brief (10-minute) web-based questionnaire about their education/occupation, their adolescent's health history, and an open-ended question about what they would like to get from PCPs for themselves and their adolescent. Adolescents who enroll in the study will receive either electronic health screening alone (i.e., control group) if

their clinic appointment occurs in the pre-I-ACT implementation period or Check Yourself (i.e., intervention group) if their clinic appointment occurs in the post-implementation period.

At baseline (T1), adolescents will be asked to complete a web-based screening survey that includes questions about guideline-recommended health risk behavior screening areas, including substance use, nutrition, physical activity, sexual behavior, depressive symptoms, and safety. The screener questions themselves are current standard of care. Adolescents will also be asked to report their age, gender, race/ethnicity, interest in discussing health risks with the PCP, and self-efficacy.

Adolescents in the control group will complete the web-based screening survey for research purposes, but neither they nor their PCP will receive feedback about their health behaviors. PCPs will screen and counsel the patient as they would normally do under usual care conditions, consistent with the current standard of care.

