During the intervention period, participating PCPs will receive adolescent-centered communication training, based on the tenets of motivational interviewing, to reinforce healthy behavior choices and to engage youth and parents to reduce risk behaviors as appropriate. PCPs will also receive three feedback reports (baseline, 2 months and 4 months) on adolescent-reported receipt of counseling on each of the target behaviors and adolescent-reported visit satisfaction and follow-up care. PCPs will not be asked to complete any study questionnaires; all of the outcome data will be gathered directly from adolescents and caregivers. Outcome data for the three feedback reports will be given to providers in aggregate form and will be void of individual identifiers.

Adolescents in the intervention group will receive full personalized motivational feedback following completion of the screening survey, both with web-based delivery. Their PCPs will receive a summary report which will include specific information on the adolescent's responses that will allow them to reinforce healthy behavior choices and implement further brief, in-person interventions for moderate to high risk adolescents. The personalized feedback to the participant and provider is consistent with current standard of care. However, the electronic method of delivery is unique to this project.

In order to administer follow-up surveys, we will ask adolescents to provide an email address, cell phone number, or phone number. One day (T2) following their PCP appointment, adolescent participants will be asked via email, text message or phone to complete a survey about their motivation for health, perception of PCP communication, and experiences. Both adolescents and their caregivers will be asked about their satisfaction with treatment during the appointment with their PCP. In addition, caregivers will be asked open-ended questions to assess the provider's delivery of caregiver education regarding strategies to reduce health risks for their child during the visit.

Three (T3), six (T4) and twelve (T5) months following their PCP appointment, adolescent participants will be asked via email, text message or phone to complete all assessments

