administered at T1 and T2 except the questionnaires related to delivery of preventive counseling, demographics, interest in discussing health risks with PCP, and self-efficacy. Additionally, adolescents will be asked about follow-up care they may have received. At T2 and T3, adolescent participants will be asked about their general satisfaction with their provider and will be asked 3-4 follow-up questions to ascertain satisfaction with the Check Yourself app and study. These surveys are not standard of care, because they are not collected as part of an appointment; however, the probability and magnitude of discomfort associated with the completion of these surveys is no greater than ordinarily encountered in daily life or during the performance of routine psychological examinations/tests or medical care.

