3.2. Measures by Construct and Time point

Tables 1 and 2 describe the study measures by construct.

Table 1: Measures used in the study, organized by construct and method.

Measures and Constructs	Time point
Moderators	
Gender, age, race, household composition, school, truancy, support, goals, interest in discussing health risks with provider	T1(A)
Number of visits with provider	T2(A)
Health Self-Efficacy	T1(A), T2 (A), T3(A), T4(A), T5(A)
Caregiver Concerns	
Guidelines for Adolescent Preventative Services Caregiver Questionnaire: adolescent health risk behavior concerns.	T1(C)
Perception of provider engagement with the caregiver	T2 (C)
Intermediary Targets	
Health Motivation (Readiness to Change Rulers): Self-report used to assess adolescent motivation for change among specific health behaviors.	T1(A), T2 (A), T3(A), T4(A), T5(A)
Adolescent Report of the Visit: adolescent-report of the PCPs' delivery of risk behavior screening and counseling based on risk level.	T2 (A)
Interval Receipt of Care: adolescent self-report of extent of follow up care.	T3 (A), T4(A), T5(A)
Main Outcomes: Satisfaction & Perception of PCP Communication	

Satisfaction Questionnaire: self-report of satisfaction with care based on items adapted from the Consumer Assessment of Healthcare Providers and Systems (CAHPS) measure.	T2(A/C)
Adolescent Perception of Patient-Centeredness: adolescent self-report of how adolescents feel about visits with their primary caregiver.	T2(A)
Main Outcomes: Health Risk Dimensions*	
Alcohol Consumption and Marijuana Use: self-report based on items about typical quantity and frequency of drinking, smoking/using tobacco, and marijuana use (each calculated separately) over the past 30 days.	T1(A), T3(A), T4(A), T5(A)
Fruit and Vegetable Screener: self-report of fruit and vegetable consumption.	T1(A), T3(A), T4(A), T5(A)
Physical Activity Screener: self-report of physical activity.	T1(A), T3 (A), T4(A),T5(A)
Sexual Risk: self-report of sexual activity, birth control, and condom use.	T1(A), T3(A), T4(A), T5(A)
Patient Health Questionnaire-9 (PHQ-9): self-report of DSM-V symptoms for depression.	T1(A), T3(A), T4(A), T5(A)
Safety: self-report to assess behaviors that contribute to unintentional injuries (e.g., seat belt use, helmet use).	T1(A), T3(A), T4(A), T5(A)

Key: T1 = Timepoint 1 (Baseline) T4 = Timepoint 4 (6 month)
T2 = Timepoint 2 (1-day) T5 = Timepoint 5 (1 year)
T3 = Timepoint 3 (3-month)
A = Adolescent survey

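### Health motivation is scheduled with a one-day score in Table 1 and the procedures but without one in Aim 1, and the Aim 1 model does not say which assessments it covers or which is the reference.

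*Combined protocol and SAP*

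**What the plan says.** Section 1.1 (Aim 1) asks for "adolescent self-report of motivation for health at baseline and 3, 6 and 12 months following the primary care visit". Its next sentence uses the one-day time point for receipt of counselling only.

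Section 3.1 describes the T1 survey as a "web-based screening survey that includes questions about guideline-recommended health risk behavior screening areas" and adds: "Adolescents will also be asked to report their age, gender, race/ethnicity, interest in discussing health risks with the PCP, and self-efficacy". Motivation is not named there. At T2 adolescents are to "complete a survey about their motivation for health, perception of PCP communication, and experiences". At T3, T4 and T5 they repeat everything "administered at T1 and T2 except the questionnaires related to delivery of preventive counseling, demographics, interest in discussing health risks with PCP, and self-efficacy". Motivation is not among those exceptions, so it continues at 3, 6 and 12 months.

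Section 3.2, Table 1, has the row "Health Motivation (Readiness to Change Rulers): Self-report used to assess adolescent motivation for change among specific health behaviors" under intermediary targets, with time points T1 through T5.

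Section 3.3.2 uses motivation to illustrate the primary mixed model. The model has an exposure term (alpha), assessment indicators (beta_k) and exposure-by-assessment terms (gamma_k), and every coefficient gets a Wald test. The indicators are defined only as marking the k-th assessment. For an adolescent enrolled after the provider's crossover, exposure is 1 in every row. Section 3.3.3 plans a subgroup analysis by baseline motivation.

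**The concern.** The meaning of alpha depends on which rows are in the model and which one is the reference, and the plan fixes neither. Aim 1 asks about motivation at 3, 6 and 12 months relative to usual care. A T1 score precedes the visit, yet it would carry exposure 1 for every post-implementation adolescent and would feed the coefficient that the plan calls the treatment effect. A T2 score is taken the day after the visit, when a short-lived response may be strongest. Depending on choices left open, the reported result could be a pre-visit imbalance, an immediate effect, an average diluted by a pre-visit row, or the longer-term effect that Aim 1 describes. Making these choices after the data are seen would leave room to pick the most favourable.

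**Working it through.** The plan gives no power or effect figure for motivation, so there is none to reproduce. The check has three steps.

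**Step 1. Schedules side by side.**

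| Source | T1 | T2 | T3 | T4 | T5 | Scores per adolescent | Maximum for about 300 |
|---|---|---|---|---|---|---|---|
| Aim 1 (1.1) | yes | no | yes | yes | yes | 4 | 4 × 300 = 1,200 |
| Procedures (3.1) | not named | yes | yes | yes | yes | 4 as named | 4 × 300 = 1,200 |
| Table 1 (3.2) | yes | yes | yes | yes | yes | 5 | 5 × 300 = 1,500 |

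Only T3, T4 and T5 appear in all three.

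**Step 2. What alpha means.** For a post-implementation adolescent compared with an unexposed one, the difference at assessment k is alpha + gamma_k, with gamma = 0 at the reference assessment. So:
- T1 modelled and used as reference: alpha is the exposed-minus-unexposed difference before the visit.
- T1 left out and T2 used as reference: alpha is the one-day effect.
- T1 and T2 both left out and T3 used as reference: alpha is the three-month effect.

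Section 3.3.3 writes the model without the gamma_k terms and says that similar models serve adolescent outcomes. In that form alpha is an average over whichever rows are modelled.

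**Step 3. Illustration of the size.** All inputs are assumptions: 150 adolescents per period (300 / 2), SD 1, no clustering, exposure constant within adolescent, complete data, equal correlation rho = 0.5 between assessments, and no true difference at T1. Scenario A has effects of 0.40, 0.20, 0.15 and 0.10 SD at T2 to T5. Scenario B has 0.40, 0.15, 0.05 and 0.

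Equal-weight average effect:

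| Rows | A | B |
|---|---|---|
| T1, T3–T5 | (0 + 0.45)/4 = 0.11 | (0 + 0.20)/4 = 0.05 |
| T2–T5 | 0.85/4 = 0.21 | 0.60/4 = 0.15 |
| T1–T5 | (0 + 0.85)/5 = 0.17 | (0 + 0.60)/5 = 0.12 |
| T3–T5 | 0.45/3 = 0.15 | 0.20/3 = 0.07 |

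Power with and without T2, for m follow-up scores: SE = sqrt[(2/150) × (1 + (m − 1)rho)/m] and power = Phi(effect/SE − 1.96).
- m = 4: SE = sqrt(0.01333 × 2.5/4) = 0.0913. A: Phi(2.328 − 1.96) = 64%. B: Phi(1.643 − 1.96) = 38%.
- m = 3: SE = sqrt(0.01333 × 2/3) = 0.0943. A: Phi(1.591 − 1.96) = 36%. B: Phi(0.707 − 1.96) = 10.5%.
- Scenario A at rho = 0.3: 76% against 43%. At rho = 0.7: 55% against 31%.

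For T1 as a covariate: the variance of a single follow-up contrast without adjustment is 1/(1 − r²) times the adjusted one. That is 1/0.75 = 1.33 at r = 0.5 and 1/0.64 = 1.56 at r = 0.6, where r is the assumed correlation of T1 with follow-up.

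**The case against.** - **Baseline.** A reader might infer that following section 3.1 leaves no pre-visit score. The text does not support that. Section 3.1 is silent at T1 and excludes nothing; it also omits household composition, school, truancy, support and goals, all of which Table 1 places at T1. Aim 1, Table 1 and the baseline-motivation subgroup all point to a T1 score. The silence is probably an incomplete description.
- **Inclusion of T2.** A reader might also infer that the model necessarily takes in T2 and averages it into the longer-term effect. It does not follow. The assessments are undefined, and the gamma_k terms in section 3.3.2 would let a T2 effect appear as its own. What stands is that the set and the reference are missing, and that the section 3.3.3 form drops those terms.
- **Analysis versus collection times.** Aim 1 may name the times to be analysed and Table 1 the times collected. That is plausible, but nothing says so, and the model section does not carry it through.
- **Illustration.** The power figures are for an equal-weight mean with no interaction, provider effect or stepped-wedge time adjustment. T2 was assumed largest, so the direction is built in. This objection stands in full.
- **Importance.** Motivation is an intermediary target, and section 3.3.2 requires an analysis plan to be presented to the study team and advisory board before each analysis. Both points limit the weight. Yet the motivation model is the template for other adolescent outcomes, and nothing requires the later plan to settle this.

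**Conclusion.** The concern holds in a limited form. The T2 conflict between Aim 1 and the other two sources is firm. The T1 gap in section 3.1 is a matter of description. The more serious defect is in section 3.3.2: with no listed assessments, no reference, and exposure coded 1 at a pre-visit row, alpha has no single meaning and need not answer the Aim 1 question. That conclusion rests on the text and the model algebra alone.

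The size cannot be fixed from the documents. In the illustration the average effect runs from 0.11 to 0.21 SD in scenario A and from 0.05 to 0.15 SD in scenario B, according to the rows used. These values depend wholly on the assumed effects and do not estimate the trial's power. The point should be settled before analysis, but it does not undermine the trial as a whole.

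**What to change.** 1. Make sections 1.1 and 3.1 and Table 1 agree: readiness rulers at T1 before any feedback is shown, then at T2, T3, T4 and T5.
2. In section 3.3.2, list the assessments modelled for motivation and name the reference.
3. Enter T1 motivation as a baseline covariate, not as an outcome row with exposure 1.
4. Define the Aim 1 motivation effect as the intervention contrast over T3 to T5, matching the follow-up times in Aim 1.
5. Report T2 as a separate immediate-effect contrast that cannot by itself support the Aim 1 conclusion.

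Adding one day to Aim 1 would also remove the wording conflict, but it would change the question and leave the T1 coding unresolved. The cost is wording in a few places, plus a few ruler items at T1 if they are not already in the survey; a pre-feedback score cannot be recovered later. No data are discarded. The downside is that the headline effect may be smaller than one that includes T2.

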2.1. Sample Size

We plan to enroll approximately 300 adolescent (age 13-18) and parent dyads who have an appointment with a participating provider affiliated with one of six participating practices in the Puget Sound Pediatric Research Network (PSPRN). We also plan to enroll approximately 30 PSPRN providers (about 5 providers per clinic).

2. Gender of Subjects

This study does not have any gender-based restrictions. However, given that women are more frequently primary caregivers and PCPs, we estimate the following gender distribution in our study population:

Adolescents: 150 Females and 150 Males

Caregivers: 240 Females and 60 Males

PCPs: 18 Females and 12 Males

3. Age of Subjects

Participants will include adult *caregivers and PCPs* (over the age of 18 years) and *adolescents* (age 13-18). As health risk behaviors typically begin in adolescence and persist into adulthood, we are targeting adolescents rather than children less than 13 years of age.

4. Racial and Ethnic Distribution

The proposed study population will include a wide cross section of adolescent patients and their caregivers, including many families of ethnoracial minority status. We will monitor diversity in our sample throughout the course of recruitment and adapt recruitment efforts as needed to assure a representative sample. The Central Puget Sound geographic area, where our study population is situated, consists of the following approximate ethnic and racial breakdown:

- 73% White
- 5% African American
- 12% Asian, Hawaiian or Other Pacific Islander
- 1% American Indian or Alaska Native
- 9% some other race (alone) or two or more races

In addition, 9% of individuals in this geographic area are of Hispanic or Latino ethnic background.

5. Inclusion Criteria

Eligible caregivers will have a child 13 to 18 years old who has an appointment with a participating provider at a PSPRN clinic and will be able to understand English.

Eligible adolescents will be 13 to 18 years old, have an appointment with a participating provider at a PSPRN clinic and will be able to understand English.

Eligible PCPs will include providers (i.e., pediatricians, family practitioners, physician assistants and nurse practitioners) affiliated with a PSPRN clinic who are following a panel of adolescent patients and will be able to understand English.

6. Exclusion Criteria

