intervention effects. Data set documentation will then be developed and distributed to the study team. Before carrying out analyses addressing each of the research questions, an analysis plan will be formally presented to the study team and Project Advisory Board so a wide range of expertise and experience is brought to bear on each work product of the team.

Some key features of the stepped wedge design require special consideration in the planned analyses. First, the design involves unidirectional cross-over from the control arm to the intervention arm for all PCPs. This has to be captured by an indicator specific to PCP and time point. Second, there are natural hierarchical structures in the data with PCPs nested within clinics, patients nested within PCPs, and repeated assessments made within patients for some outcomes, such as health risk behaviors. Because different patient samples will be surveyed at each time point, within patient correlation over time should not be strong. Still, clustering at the clinic and PCP-levels needs to be examined in all analyses. Third, secular time trends need to be carefully examined and separated from the intervention effect. Based on these considerations, we will focus on model-based approaches (linear or generalized linear mixed effects models) for the main analyses, in addition to standard hypothesis testing techniques.

Aim 1 will compare intermediary targets at all clinics before and after the intervention using an analytic approach that both accounts for design features, repeated assessments within adolescents, time trends in these target behaviors during study period and adjust for potential confounders. For this aim we will use patients as the units of analysis. We will consider outcomes at the level of the patient (adolescent reported motivation for health and provision of appropriate preventive counseling).

Our primary analysis will be based on a set of mixed effects regression models. As an illustration, let's consider the adolescent self-reported health motivation (readiness to change, as other adolescent reported outcomes can be modelled in a similar fashion. Specifically, we will consider the following regression model:

$$Y_{ijk} = \mu + \alpha X_{ijk} + \beta_k T_k + \gamma_k X_{ijk} * T_k + b_i + b_{ij} + \varphi \text{Covariates} + \varepsilon_{ijk},$$

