in which Y_{ijk} denotes the health motivation reported by j th patient within i th provider at k th time interval, X_{ijk} is a binary indicator of exposure to the intervention for the provider and the predictor of interest, T_k is a binary indicator of the k th assessment, b_i and b_{ij} are PCP and adolescent specific random effects that account for the within PCP and within adolescent correlations, and ε_{ijk} is the error term. Additional patient-level or PCP-level confounding variables can be adjusted in the model as well.

With this model, the fixed effects α captures the treatment effects on mean responses and time-by-intervention interaction coefficients γ_k 's captures the treatment effects across time. Fixed effects β_k 's aim to capture any temporal trend or learning effects. Using this approach, both within-adolescents and between adolescents information will be used to estimate the treatment effects. All coefficients will be tested using Wald test. Also note this

model framework is flexible enough that a patient can be enrolled at any time during the study and the model can accommodate different numbers of post-intervention assessments. For example, for an adolescent enrolled after his/her PCP has received intervention, all X_{ijk} 's would take value 1 for that subject.

We will apply linear mixed effects models for Gaussian outcome Y_{ijk} , and generalized linear mixed effects models for other types of outcomes (e.g., logistic model for binary outcome).

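### The 3-, 6- and 12-month contrasts are described as against usual care, but control PCPs cross over during follow-up and the plan does not say how those controls are coded

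*Combined protocol and SAP*

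**What the plan says.** Aim 2 in section 1.1 names the comparator for the risk behaviours, ending with "depression compared to a usual care group at baseline and 3, 6, and 12 months after the primary care visit".

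Section 3.1 rolls the intervention out clinic by clinic, in random order, over intervals shown only in Figure 1. An adolescent is a control if "their clinic appointment occurs in the pre-I-ACT implementation period". Controls get no feedback from the baseline survey, and neither do their PCPs. Both groups are then surveyed "Three (T3), six (T4) and twelve (T5) months following their PCP appointment".

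Section 3.3.2 states that "the design involves unidirectional cross-over from the control arm to the intervention arm for all PCPs", and asks for an exposure indicator that varies by PCP and by time. In the longitudinal model, X_ijk "is a binary indicator of exposure to the intervention for the provider and the predictor of interest", and it carries the assessment index k. The coding is spelled out for one case only: an adolescent enrolled after the PCP has crossed has X = 1 throughout. Nothing is said about an adolescent enrolled before.

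Table 1 also lists "Interval Receipt of Care: adolescent self-report of extent of follow up care" as an outcome at T3, T4 and T5.

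**The concern.** Controls remain patients of clinics that later adopt the intervention. A control who goes back to his or her PCP after the crossover sees someone trained in I-ACT. The comparator at 3, 6 and 12 months is then partly usual care and partly delayed exposure, and the mix shifts toward exposure as follow-up lengthens. Reported follow-up care is the outcome most directly touched, because a trained PCP may be the one who gives it.

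Nothing in the available text stops control follow-up at the clinic's crossover, delays crossover until follow-up ends, or qualifies the late conclusions. A benefit that lasts could be reported as fading by 12 months. In the extreme, no control would still have an untrained PCP at T5, and a 12-month effect against continued usual care could not be estimated.

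**Working it through.** The documents give no figure for the share of controls whose PCP crosses over, and no power calculation, so there is nothing of the plan's own to reproduce.

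**1. Share of controls whose PCP has crossed.** From the documents: six clinics (section 2.1, "one of six participating practices"), sequential rollout, assessments at 3, 6 and 12 months. Assumed: one clinic crosses per step of s months, so clinic c crosses at month c × s, and control visits are spread evenly from month 0 to that date. The share crossed within m months of the index visit is

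Σ min(m, c × s) / Σ (c × s), for c = 1 to 6.

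Example with s = 3: crossovers at months 3, 6, 9, 12, 15 and 18, which sum to 63.
- 3 months: 6 × 3 = 18; 18/63 = 29%.
- 6 months: 3 + 5 × 6 = 33; 33/63 = 52%.
- 12 months: 3 + 6 + 9 + 3 × 12 = 54; 54/63 = 86%.

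| Step (months) | Last crossover (month) | 3 months | 6 months | 12 months |
|---|---|---|---|---|
| 2 | 12 | 40% | 71% | 100% |
| 3 | 18 | 29% | 52% | 86% |
| 4 | 24 | 21% | 40% | 71% |
| 6 | 36 | 14% | 29% | 52% |
| 9 | 54 | 10% | 19% | 37% |

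With two clinics per step, the 12-month share is 100% for 3- or 4-month steps and 83% for 6-month steps. It is 100% whenever the last crossover comes within 12 months of first enrolment.

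**2. If X is fixed at the index visit.** Let r be the proportion of crossed controls who return to the trained PCP, and p the fraction of the full effect that such a visit gives. The contrast keeps 1 − share × r × p. Both r and p are assumed. For steps of 2, 3 and 4 months:
- 12 months, r = 0.3, p = 0.5: 0.850, 0.871, 0.893.
- 12 months, r = 0.5, p = 0.5: 0.750, 0.786, 0.821.
- 3 months, same inputs: 0.939, 0.957, 0.968 and 0.899, 0.929, 0.946.

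Shrinkage is thus 11–25% at 12 months against 3–10% at 3 months. With r = 0.3 and p = 0.25 it is 5–8% at 12 months. For a contrast assumed to have 80% power at two-sided 5%, power after shrinkage a is Φ(2.802 × (1 − a) − 1.960): 66% at a = 0.15 and 56% at a = 0.25. These are illustrations under fixed X only.

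**3. If X switches with the PCP.** The controls still coded 0 at T5 are those whose PCP has not crossed: 0% for 2-month steps, 14% for 3-month steps (9/63, all from the last two clinics) and 29% for 4-month steps (24/84). If none remain, X × T_k equals T_k at T5 for every adolescent. The interaction γ_k then cannot be separated from the time effect β_k, and the 12-month effect α + γ_k is not identified. Switching also codes as exposed those controls who had no Check Yourself feedback at the index visit and may never have returned to the PCP.

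**4. The passages side by side.** Sections 1.1 and 3.1 group adolescents by index visit. Section 3.3.2 defines exposure by PCP and time. These give different 12-month contrasts.

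**The case against.** The strongest reply is that the planned model already deals with crossover. Section 3.3.2 wants exposure to vary by PCP and time, allows the number of assessments after the intervention to differ between adolescents, and draws on information within as well as between adolescents. The most natural reading is that X switches, so post-crossover control assessments count as exposed and X = 0 stays pre-crossover usual care. The shrinkage figures would then not apply. This stands as far as it goes: those figures describe fixed X only. But the coding is not stated for adolescents enrolled before crossover, and switching has the faults shown in step 3. The same text also shows that crossover is expected to fall inside follow-up, even without Figure 1.

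A reader might infer that by 12 months most or all controls are cared for by a trained PCP. The documents do not support that. The shares above count controls whose PCP has crossed, and exposure needs a return visit. With 30–50% returning, 21–50% of controls would have seen a trained PCP by 12 months under 2- to 4-month steps (0.714 × 0.3 to 1.000 × 0.5). No text requires follow-up care to be with the same PCP.

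Nor is the comparator usual care at one day only. Under those steps, 60–79% of controls still have an uncrossed PCP at 3 months. A recently crossed PCP will also not have had all three feedback reports, which section 3.1 places at baseline, 2 and 4 months.

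Finally, the index-visit contrast keeps a meaning. Section 3.1 ties the Check Yourself feedback and the PCP's summary report to the baseline survey and index visit, so a control who returns later would mainly meet the training component.

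**Conclusion.** The point holds as a mismatch between the comparator named in section 1.1 and the one the design can deliver at T3 to T5, made worse by an exposure indicator left undefined for controls whose PCP crosses during follow-up. Neither coding yields a clean 12-month contrast with usual care: one dilutes it, and the other misclassifies exposure and may leave it unestimable.

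The size depends on rollout spacing, which is in a figure not shown. With one clinic per step, more than half of controls have a crossed PCP by 12 months for every step length examined up to 6 months (52–100%), but 37% at 9 months. Even 37% would make the usual care label inaccurate at T5. That the 12-month effect cannot be estimated is conditional, not established: under switching X it requires every control PCP to have crossed by T5. Return rate, partial effect and baseline power are assumptions. The one-day outcomes are not affected.

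**What to change.** 1. In section 3.3.2, define X for the main T3–T5 analysis by the PCP's status at the index visit. In section 1.1, name that contrast as index visit after versus before PCP crossover, with control PCPs crossing over during follow-up. Keep the description as versus usual care for T2 and for control assessments dated before the clinic's crossover.
2. Report, for each time point, how many control assessments fall before and after crossover. If none precede crossover at T5, state that a 12-month effect against continued usual care is not estimable.
3. Add a sensitivity analysis limited to control assessments dated before crossover, adjusted for clinic and calendar time, and run it only where enough such assessments exist. A calendar term is needed because T_k is defined by assessment. It should not lean on the inverse probability weighting planned in section 3.3.1 for missing data: given clinic and visit date, this exclusion is deterministic, so some controls have no chance of being retained and no weight can stand in for them.

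The cost is wording plus one analysis from survey and crossover dates the study should already hold. No new participants or data are needed. The price is a narrower 12-month claim and a less precise sensitivity analysis. Any shrinkage or power figures should be shown only as illustrations under fixed X.
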